# Effectiveness of a Hydroxyapatite-Containing Toothpaste Versus Mouthwash in Preventing White-Spot Lesions During Fixed-Appliance Orthodontic Treatment: A Randomized Clinical Trial

## Introduction:

Orthodontic treatment is widely recognized as an effective approach to improve dental and facial aesthetics, which play a crucial role in overall attractiveness and psychosocial well-being. A recent systematic review and meta-analysis confirmed that orthodontic therapy enhances facial attractiveness by approximately 9% compared with untreated individuals. However, despite these aesthetic benefits, fixed appliance therapy is associated with several side effects, most notably the development of white spot lesions (WSLs) (Kouskoura et al., 2022).

The placement of fixed orthodontic appliances significantly increases dental biofilm accumulation around brackets and wires. Patients undergoing fixed-appliance orthodontic treatment show a higher concentration of plaque, particularly on the labial surfaces of anterior teeth, compared to pre-treatment levels. This accumulation is attributed to the brackets acting as retention sites, making oral hygiene maintenance more challenging and increasing the risk of enamel demineralization, gingival inflammation, and the WSLs (Kozak et al., 2021).

WSLs represent the earliest stage of dental caries, characterized by subsurface demineralization of the enamel, which appears as opaque, non-cavitated white areas

on the tooth surface. These lesions indicate the onset of enamel decay and may progress to cavities if left untreated (**Lopes et al., 2024**).

Fluoride has been widely used in toothpastes and mouthwashes for caries prevention; however, excessive or prolonged exposure has been associated with potential adverse effects. These include dental fluorosis, characterized by white or brown discoloration of teeth (**Choi et al., 2012**).

Therefore, hydroxyapatite (HAP)-containing oral care products have emerged as a safe and effective alternative. Clinical evidence demonstrates that HAP can remineralize enamel, reduce the formation of WSLs, and provide preventive outcomes comparable to or better than fluoride, without the associated systemic or local side effects (**Amaechi et al., 2019**). Therefore, incorporating HAP-based toothpaste or mouthwash into daily oral hygiene routines during orthodontic treatment offers a biocompatible and reliable strategy to minimize enamel demineralization and improve clinical outcomes.

Hydroxyapatite (HAP)-containing oral care products have been increasingly recognized for their ability to remineralize enamel and reduce the formation of WSLs. Clinical evidence confirms that HAP-containing toothpaste can re-mineralize enamel lesions effectively while enhancing tooth brightness without adverse effects (**BMC Oral Health, 2022; Paszyńska et al., 2023**). In addition, a mouthwash can significantly reduce interdental gingival bleeding, highlighting its role as an effective adjunct to mechanical oral hygiene (**Saliasi et al., 2018**). Systematic reviews and meta-analyses have reported that mouth rinses can provide a benefit beyond mechanical oral hygiene alone in preventing plaque accumulation and gingivitis (**Araujo et al., 2015**). These findings underscore the relevance of incorporating both HAP-based oral care products and mouthwashes as preventive and supportive measures in modern dental care protocols.

## **Research Question:**

In patients undergoing fixed-appliance orthodontic treatment, which intervention hydroxyapatite-containing toothpaste, hydroxyapatite mouthwash, or conventional oral hygiene is most effective in preventing the development of white-spot lesions?

## **Aim and Objectives:**

### **Aim:**

To evaluate and compare the effectiveness of a hydroxyapatite-containing toothpaste, a hydroxyapatite-containing mouthwash, and conventional oral hygiene products in preventing or reducing the incidence of white spot lesions (WSLs) during fixed-appliance orthodontic treatment.

### **Primary Objectives:**

To evaluate the preventive effectiveness of two enamel remineralizing methods compared to the conventional method in reducing the risk of WSLs on the labial surfaces of upper and lower incisors, and canine teeth during six months of orthodontic treatment by monitoring:

1. Severity of WSLs using the Gorelick index.
2. Enamel integrity and early demineralization using Diagnodent Pen scores.
3. Incidence of WSLs assessed using photographic documentation.

### **Secondary Objectives:**

1. To assess oral health status using Gingival Bleeding Index (GBI), and Plaque

Index (PI).

2. To measure salivary pH changes over the study period.

### **Hypothesis:**

Null Hypothesis (H0):

There is no significant difference in the incidence or severity of white-spot lesions among patients using hydroxyapatite toothpaste, hydroxyapatite mouthwash, or conventional oral hygiene during fixed-appliance orthodontic treatment.

Alternative Null Hypothesis (H1):

There is a significant difference in the incidence and severity of white-spot lesions among patients using hydroxyapatite toothpaste or hydroxyapatite mouthwash, with either intervention potentially showing superior preventive effectiveness.

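### Three unranked primary outcomes, only one of them sized, and an alternative hypothesis that does not match the null: the protocol does not say which outcome decides the trial

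*Protocol*

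**What the plan says.** Protocol, Primary Objectives, sets the comparison as "two enamel remineralizing methods compared to the conventional method in reducing the risk of WSLs". It then numbers three measures without ranking them: "Severity of WSLs using the Gorelick index", "Enamel integrity and early demineralization using Diagnodent Pen scores" and "Incidence of WSLs assessed using photographic documentation".

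The Aim compares the toothpaste, "a hydroxyapatite-containing mouthwash, and conventional oral hygiene products in preventing or reducing the incidence of white spot lesions". Its outcome is incidence alone. The Research Question asks which of the three regimens best prevents lesions from developing.

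The null hypothesis reads "There is no significant difference in the incidence or severity of white-spot lesions among patients using hydroxyapatite toothpaste, hydroxyapatite mouthwash, or conventional oral hygiene". The alternative reads "There is a significant difference in the incidence and severity of white-spot lesions among patients using hydroxyapatite toothpaste or hydroxyapatite mouthwash" and goes on "with either intervention potentially showing superior preventive effectiveness".

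Sample Size bases 80% power at the 5% level on a 1-unit difference in the Gorelick index. It sets 75 participants, 25 per group, and says that this allows for dropout. It gives no SD, dropout rate, visit or between-group comparison, and no rule for combining teeth. The section on photography and the Gorelick index scores the photographs from 0 to 4.

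**The concern.** When several outcomes are primary and none leads, a favourable result on any of them could later be presented as the main result of a trial with 80% power. That figure was set for one outcome only. The outcome named in the Aim is not the one that was sized, and one of the listed primary measures appears in neither hypothesis. The hypotheses might have settled which result counts, but they do not fit each other or the primary objective. Once data have been seen, the lead outcome can no longer be chosen credibly.

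**Working it through.** **1. The sections side by side**

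| Protocol section | Outcome | Groups |
|---|---|---|
| Research Question | development of lesions | all three |
| Aim | incidence | all three |
| Primary Objectives | Gorelick severity; DIAGNOdent; photographic incidence | two hydroxyapatite methods versus conventional |
| Null hypothesis | incidence *or* severity | all three |
| Alternative hypothesis | incidence *and* severity | two hydroxyapatite groups named |
| Sample Size | Gorelick index, 1 unit | not stated |

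Sample Size says which outcome its figures belong to. No section says that this outcome decides the trial.

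**2. The plan's own figure.** With a normal approximation and a two-sided 5% level (sidedness is not stated), n per group = 2 × SD² × (1.960 + 0.842)² / 1² = 2 × SD² × 7.85.

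- SD 1.0: 15.7, so 16 per group
- SD 1.25: 24.5, so 25 per group
- SD 1.5: 35.3, so 36 per group

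Twenty-five per group gives 80% for SDs up to about 1.26 with no dropout, or up to about 1.13 if 20 per group complete (assumed). Without an SD and a dropout rate, the 75 can be neither reproduced nor refuted. In any case it concerns the Gorelick score only.

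**3. The two hypotheses.** The null denies any difference in either outcome among three groups. The alternative, read literally, asserts a difference in both outcomes among two groups. A difference in severity alone, or one only between a hydroxyapatite group and the conventional group, then falls under neither. The second case is exactly what Primary Objectives sets out to find.

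**4. Incidence, as an illustration.** The protocol gives no control incidence, target reduction, unit of analysis or number completing, so all of these are assumed: incidence per participant, control rates of 30%, 50% and 70%, risk halved, and 25 or 20 per group analysed. The comparison is one hydroxyapatite group versus control, two-sided 5%, by the pooled normal approximation:

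power = Φ{ [ (p₁ − p₂) − 1.96 × √(2p̄(1 − p̄)/n) ] / √[ (p₁(1 − p₁) + p₂(1 − p₂))/n ] }

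For 50% versus 25% with n = 25, p̄ = 0.375. The null standard error is √(0.46875/25) = 0.137, the alternative standard error is √(0.4375/25) = 0.132, and (0.25 − 0.268)/0.132 = −0.139. Power is Φ(−0.139), about 45%.

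| Control vs hydroxyapatite | 25 per group | 20 per group |
|---|---|---|
| 30% vs 15% | 24% | 20% |
| 50% vs 25% | 45% | 37% |
| 70% vs 35% | 71% | 61% |

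To reach 80% with 25 per group, incidence would have to fall from 50% to about 14%, or from 70% to about 31%.

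**5. Sensitivity of the illustration.** Exact enumeration with 25 per group gives 26%, 48% and 76% for the chi-square test, and 15%, 36% and 65% for Fisher's test. Counting teeth also changes the values. Take 12 teeth per participant (eight incisors, four canines), 25 participants per group, an assumed intraclass correlation of 0.1 to 0.5 and a design effect of 1 + 11 × ICC. Then 30% versus 15% gives 86% down to 41%, and 50% versus 25% gives 99% down to 71%. Rates per tooth may be lower, and 20% versus 10% gives 66% down to 27%.

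**The case against.** The strongest reply is that Sample Size does tie the 80% and the 5% to the Gorelick index. That is correct. A reader might infer that the protocol leaves open which outcome those figures were computed for, and it does not. What stays open is whether that outcome leads, and whether the 5% also covers the other two.

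A second reply is that the wording of the alternative hypothesis is harmless. The null, the Research Question, the Aim and the Primary Objectives all include the conventional group, and the same sentence ends by speaking of superior prevention. This also stands: it is probably a drafting slip. A reader might take it to mean that the control comparison will not be tested, or that success formally requires both incidence and severity. The protocol states neither as a decision rule, so the slip inflates no error rate and lowers no power.

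Third, outcomes 1 and 3 overlap because the Gorelick index is scored on photographs. They do overlap, but a 1-unit difference in severity is not a difference in the share of participants with a lesion.

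Fourth, a reader might infer that multiplicity is uncontrolled. The document cannot show that, because such a procedure may be in a statistical analysis plan that was not available.

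Finally, incidence could be made the lead outcome instead, since the Aim names it. That would also remove the ambiguity, but it would need its own sample size and a control incidence that the protocol does not give.

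**Conclusion.** The point holds in this form: three measures are called primary without rank, one is sized, and the other sections point to different ones. The protocol does not say whether the sized outcome decides the trial. The stated 80% does not carry over to incidence, or to the alternative hypothesis as written, which also calls for a difference in incidence. This should be fixed before data are seen.

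The size of the gap cannot be fixed from the document. On the assumptions shown, 25 per group gives 24% to 71% power for a halved per-participant incidence, and 20 per group gives 20% to 61%. A different test or a per-tooth unit changes these values, in some cases to above 80%. They show only that power for Gorelick severity says little about power for incidence. The mismatch between the hypotheses is a minor wording repair, and the rating does not rest on it.

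**What to change.** 1. Name the Gorelick score, the only outcome sized, as the single primary outcome. State the visit (for example 6 months, the end of follow-up in Primary Objectives) and how the teeth are combined into one score per participant, because Sample Size gives neither. Make DIAGNOdent and photographic incidence secondary. Align Research Question, Aim, Primary Objectives and Hypothesis with this, and say in Sample Size that the 80% applies to the Gorelick outcome only.
2. Restate the null as no difference in that score among the three groups, and the alternative as a difference between at least two of them. State that a preventive claim rests on a hydroxyapatite group versus the conventional group, and report toothpaste versus mouthwash as a separate comparison.

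The cost is rewording of those sections, and two outcomes lose primary status, including the incidence named in the Aim. The change itself needs no extra participants. The multiplicity procedure for the pairwise comparisons can stay in the statistical analysis plan.

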## **Methodology**

### **Study Design:**

This study is designed as a multicenter, parallel, randomized clinical trial. Each participant will be randomly assigned to one of the three groups:

- **Group A:** Participants will be instructed to brush their teeth three times daily with the hydroxyapatite-containing toothpaste and to rinse twice daily with a placebo mouthwash.
- **Group B:** Participants will be instructed to brush their teeth three times daily with a conventional fluoride toothpaste and to rinse twice daily with a hydroxyapatite-containing mouthwash.

- **Group C:** Participants will be instructed to brush their teeth three times daily with a conventional fluoride toothpaste and to rinse twice daily with a placebo mouthwash.

All interventions and assessments will be conducted throughout the study period. The same participant (orthodontic patient) will be evaluated at baseline (before bonding) and at 1, 3, and 6 months after the placement of orthodontic appliances.

Participants will receive standardized oral hygiene instructions, and all assessments of white-spot lesions will be performed using Diagnodent Pen, Gorlick index (GI), digital photographs, Gingival Bleeding Index (GBI), Plaque Index (PI), and salivary pH measurements to minimize variability and ensure consistent data collection.

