### **Procedure / Intervention:**

- **Group A:** Participants will be instructed to brush their teeth three times daily with the hydroxyapatite-containing toothpaste and to rinse twice daily with a placebo mouthwash.
- **Group B:** Participants will be instructed to brush their teeth three times daily with a conventional fluoride toothpaste and to rinse twice daily with a hydroxyapatite-containing mouthwash.
- **Group C:** Participants will be instructed to brush their teeth three times daily with a conventional fluoride toothpaste and to rinse twice daily with a placebo

mouthwash.

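### Groups A and B differ in both toothpaste and rinse, so A versus B compares whole regimens, not hydroxyapatite toothpaste against hydroxyapatite mouthwash

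*Protocol*

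**What the plan says.** The Study Design section of the Protocol defines three arms, and the Procedure / Intervention section repeats them without change:

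- Group A: participants "brush their teeth three times daily with the hydroxyapatite-containing toothpaste and to rinse twice daily with a placebo mouthwash".
- Group B: participants "brush their teeth three times daily with a conventional fluoride toothpaste and to rinse twice daily with a hydroxyapatite-containing mouthwash".
- Group C: participants "brush their teeth three times daily with a conventional fluoride toothpaste and to rinse twice daily with a placebo" mouthwash.

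The Mouthwash Protocol describes the placebo rinse as water with flavouring and lists no fluoride.

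The stated purpose names A and B by their HAP product only. The title reads "Effectiveness of a Hydroxyapatite-Containing Toothpaste Versus Mouthwash in Preventing White-Spot Lesions". The Research Question asks which of HAP toothpaste, "hydroxyapatite mouthwash, or conventional oral hygiene is most effective in preventing the development of white-spot lesions". The Aim is "To evaluate and compare the effectiveness of a hydroxyapatite-containing toothpaste, a hydroxyapatite-containing mouthwash, and conventional oral hygiene products". The alternative hypothesis mentions only the two HAP products and allows either to be superior. The Primary Objectives are narrower: "To evaluate the preventive effectiveness of two enamel remineralizing methods compared to the conventional method", that is, A versus C and B versus C.

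No visible text gives the fluoride content of the HAP toothpaste. The Introduction presents HAP products as an alternative to fluoride that can "provide preventive outcomes comparable to or better than fluoride, without the associated systemic or local side effects", and the Blinding section contrasts HAP-containing with conventional formulations.

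**The concern.** A reader of the title and the alternative hypothesis expects A versus B to show whether HAP prevents lesions better in a toothpaste or in a mouthwash. That reading needs A and B to be alike in everything but the vehicle of HAP, and they are not. Moving from A to B swaps the HAP rinse in for the placebo rinse and also swaps a fluoride paste in for the HAP paste. The Introduction itself says that fluoride is widely used to prevent caries, and the Exclusion Criteria rule out recent topical fluoridation, so by the Protocol's own account the companion paste in B is not inert.

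At stake is the headline conclusion. If the HAP toothpaste contains no fluoride, B could come out ahead although HAP works equally well in both forms, or a real advantage of the toothpaste form could be hidden or reversed. More participants would not help, because the problem lies in what the arms contain and not in precision.

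**Working it through.** **Inputs.** Arm contents come from Study Design and Procedure / Intervention. The Photography and Gorelick Index Assessment section gives the direction of the score (0 is no lesion, 4 is cavitation, so higher is worse). The Sample Size section gives the design difference of 1 Gorelick unit with 25 per group. That section states no SD, so the 25 cannot be reproduced, but nothing below depends on it. All effect sizes below are assumptions.

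**Step 1: what the arms identify.** Let *f*, *p* and *r* be the reductions in mean score from fluoride paste, HAP paste and HAP rinse, first taken as additive. The comparison the title implies is *p − r*.

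*HAP paste fluoride-free.* The reductions are A = *p*, B = *f + r*, C = *f*. The arms give two independent contrasts:

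- A − C = *p − f*
- B − C = *r*

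Their coefficients on (*f*, *p*, *r*) are (−1, 1, 0) and (0, 0, 1), which have rank 2. Adding the target (0, 1, −1) raises the rank to 3 (the determinant is 1), so *p − r* cannot be estimated from these arms.

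*Fluoride matched in the HAP paste.* Now A = *f + p*, so A − C = *p* and B − C = *r*. The target is their difference, the rank stays at 2, and *p − r* can be estimated.

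**Step 2: a check by example (fluoride-free case).**

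| Assumed *p* | Assumed *r* | Assumed *f* | A − C | B − C | A − B | True *p − r* |
|---|---|---|---|---|---|---|
| 0.5 | 0.5 | 0 | 0.5 | 0.5 | 0 | 0 |
| 1.0 | 0.5 | 0.5 | 0.5 | 0.5 | 0 | 0.5 |

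Both rows give the same data in all three arms, yet the difference between HAP forms is zero in one and half a unit in the other.

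**Step 3: size of the shift (fluoride-free case).** HAP and fluoride effects may overlap, so let *n* be the extra reduction that fluoride gives on top of the HAP rinse in B. Full additivity is the case *n = f*, and complete overlap is *n = 0*. The reduction is *p* in A and *r + n* in B. In mean score, where positive means A is worse:

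A − B = *n − (p − r)*

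| Assumed *n* | A − B if *p − r* = 0 | Share of the 1-unit design difference | A − B if *p − r* = 0.2 |
|---|---|---|---|
| 0 | 0 | 0% | −0.20 |
| 0.1 | +0.10 | 10% | −0.10 |
| 0.25 | +0.25 | 25% | +0.05 |
| 0.5 | +0.50 | 50% | +0.30 |

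In the last column the toothpaste form is truly better by 0.2 units, and the observed ranking reverses once *n* exceeds 0.2.

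**Step 4: the comparisons with control.** A versus C and B versus C remain valid randomised comparisons. With a fluoride-free HAP paste they answer different questions. A versus C replaces fluoride toothpaste with HAP toothpaste, and B versus C adds a HAP rinse to fluoride toothpaste. Setting the two results side by side therefore does not recover the comparison of forms either.

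**The case against.** The strongest reply is that the harm rests on a fact the Protocol does not state. If the HAP toothpaste carries the same fluoride as the conventional one, the shift disappears. The two cues are indirect: the Introduction speaks of HAP products in general, and the contrast in the Blinding section covers toothpaste and mouthwash together, where the non-HAP rinse is a placebo and not a fluoride product. A figure in the Mouthwash Protocol is also not visible. This stands, and the conclusion is conditional for that reason.

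Second, the Protocol never says that it wants the effect of product form in isolation. The Research Question can be read as a pragmatic ranking of assigned interventions that are fully defined elsewhere, and randomisation supports such a ranking. That reading is legitimate, but no section adopts it. The title, aim and alternative hypothesis name A and B by the HAP product alone, and the different companion paste is not acknowledged.

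Third, the primary objective compares each method with control and is not invalidated. That is right, but it does not cure the title, question, aim and hypothesis.

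Fourth, the sizes are assumed. They are, and the range includes zero. They show how the contrast behaves and do not estimate a bias. Replacing additive *f* by *n* does not rescue the comparison of forms, because *n* is a further unknown.

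Finally, the instructed frequency of HAP use (three times daily in A, two in B) is openly stated and is no error. It does mean that A versus B compares regimens even with matched fluoride.

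**Conclusion.** The concern holds. A and B differ in both products, B's companion paste is active, and the headline wording treats the contrast as HAP toothpaste against HAP mouthwash. If the HAP toothpaste is fluoride-free, which the text suggests but does not establish, the difference between HAP forms cannot be estimated from these arms, and A versus B is shifted in favour of B by *n*. The documents give no value for *n*; assumed values of 0 to 0.5 units correspond to 0% to 50% of the design difference. The shift is zero if HAP and fluoride effects overlap completely, or if fluoride is matched and overlaps equally with HAP in both arms.

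The ranking of the three whole regimens and both comparisons with control are unaffected. This is a mismatch between the claim and the arms that should be corrected; the trial itself can proceed with the arms as they are.

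**What to change.** Keep the arms and products and change the wording.

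1. In the title, Research Question, Aim and Hypothesis, describe A versus B as a comparison of two whole regimens: HAP toothpaste with placebo rinse against fluoride toothpaste with HAP rinse. Note that the regimens also differ in instructed frequency of HAP use, and state that no conclusion will be drawn about which HAP product form is better.
2. If the HAP toothpaste is fluoride-free, describe A versus C as substitution of HAP for fluoride toothpaste, and B versus C as addition of HAP mouthwash to fluoride toothpaste. State the fluoride content of both HAP products so that the reader can verify this wording.

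The cost is an edit to four places and one line on composition, with a narrower headline claim. Sample size and the contrasts in the Primary Objectives do not change.
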